• Subgroups formed by **anti-N antibody status** (positive versus negative at study entry), and bivariate subgroups formed by the combinations of anti-N Ab status and plasma antigen or viral RNA levels. Anti-N antibody levels are measured using a SARS-CoV-2

antibody assay by **BioRad** (Hercules, CA, USA) measuring total (IgA, IgG, and IgM) anti-nucleoprotein. For the subgroup analyses, participants with anti-N levels <1 will be considered "anti-N Ab negative", those with levels \geq 1 will be considered "anti-N Ab positive".

Comment: Results of the BioRad anti-N antibody measurement are defined in terms of "specimen ratios". According to the manufacturer, specimen ratios less than 0.8 are considered negative, those with a specimen ratio between 0.8 and 1.0 are considered equivocal, and those \geq 1.0 are considered positive for the presence of anti-SARS-CoV-2 antibodies. For the subgroup analyses, participants with negative and equivocal anti-N Ab results will be combined and referred to as "anti-N negative".

 Subgroups formed by quantitative anti-Spike IgG (Quanterix) antibody status (positive versus negative), and bivariate subgroups formed by the combinations of anti-Spike IgG status and plasma antigen or viral RNA levels. Specimens with antibody levels < 770 ng/mL will be considered "anti-Spike IgG antibody negative", those with levels ≥ 770 ng/mL will be considered "anti-Spike IgG positive".

Motivation for the hypotheses:

In the TICO bamlanivimab trial, there was no difference in time to sustained recovery by day 90, RRR=0.99 (95% CI: 0.79 to 1.22), p=0.89. However, the treatment effect varied by nAb status at baseline; among patients who were nAbs negative and positive at entry, the RRRs were 1.24 (95% CI: 0.90-1.70) and 0.74 (95% CI: 0.54-1.00), respectively (p=0.02 for differential treatment effect). This means, there was a trend towards benefit with bamlanivimab among those who did not have endogenous nAbs at study entry, while time to sustained recovery was longer with bamlanivimab compared to placebo among those who already had endogenous nAbs. Moreover, among those who were nAb negative, the difference between bamlanivimab and placebo was more evident if plasma antigen or nasal-swab viral RNA were above the median levels at study entry. Results for subgroups by anti-N Ab status had a similar pattern, but less pronounced.

Motivation for safety analyses by nAb status:

In an analysis of the combined data for first three nMAbs investigated in TICO (bamlanivimab, sotrovimab, and BRII-196/198), the risk of the composite safety outcome of *death*, SAE, organ failure, or serious infections through Day 90 was similar in the "active" versus placebo arms, but a safety signal was identified among participants with pre-existing endogenous neutralizing antibodies (nAbs). Specifically, the risk of the composite outcome at day 90 was 25.3% in the (pooled) active arms compared with 27.2% in the (pooled) placebo groups, HR=0.95 (95% CI: 0.72 to 1.25). The treatment effect on the composite safety outcome at day 90 differed by nAb serostatus at baseline, however; in participants who were nAb negative at baseline, HR=0.72 (95% CI: 0.50 to 1.02) (HR<1 favors the "active" group), and HR=1.42 (95% CI: 0.91 to 2.22) (favoring the placebo group) among those who were nAb positive at baseline, nominal p-value for interaction p=0.02. In the placebo group, the rate for the composite safety endpoint was higher among those who were nAb negative at baseline compared with those who were nAb positive (33% versus 20%, respectively); those who were nAb negative at baseline were sicker from COVID-19 at study entry and also had a lower chance of *sustained recovery*. Mortality followed a similar pattern as the composite outcome; there was no evidence for a difference between the active versus placebo groups in the overall analyses (pooled across the three nMAbs), HR=1.13 (95% CI:0.67 to 1.88), while the treatment effect on mortality differed according to baseline nAb status, with HR=0.72 (95% CI: 0.39-1.33) (HR<1 favoring the active arm) among those who were nAb negative, compared to HR=3.64 (95% CI: 1.05 to 12.65) among those who were nAb positive.

10 Interim Monitoring Guidelines for the DSMB

Each investigational agent versus placebo comparison will be treated as a separate clinical trial; stopping boundaries will be derived to allow for multiple interim looks, but will not be additionally inflated to adjust for simultaneous analysis of multiple investigational agents, except when explicitly stated in the agent-specific protocol appendix and statistical analysis plan.

The DSMB will be asked to recommend early termination or modification only when there is clear and substantial evidence of a treatment difference (unless a trial is stopped for futility).

10.1 Early Assessment of Safety

For investigational agents with minimal pre-existing data, the pace of enrollment will be initially restricted and the DSMB will be asked to review safety data for the first 20 to 30 participants before increasing the pace of enrollment.

Subsequently, the DSMB will carry out regular reviews of safety data reports. These reports will include summaries of infusion–related events, grade 1-4 AEs, SAEs, organ failure, serious infections, and deaths, including the primary safety outcome at Day 5, and Day 28. Event listings for incident grade 3 and 4 AEs, SAEs, organ failure and serious infections, SUSARs, UPs and deaths will be provided (events that were reported since the previous review will be marked). Narratives will be provided for selected SAEs, SUSARs or UPs, particularly those judged related to study treatment. Analyses are described in section 7.

Monitoring boundary for harm:

- Until the first 300 participants are enrolled (150 per study arm) and the early futility analysis is conducted, the treatment groups will also be compared for the "pulmonary" and "pulmonary+" ordinal outcomes at Day 5, using a proportional odds model stratified by study pharmacy and pulmonary+ outcome category at baseline. A Haybittle-Peto boundary with 2.5 standard deviation (SD) for the first 50 participants enrolled and 2.0 SD afterwards will be used as a guideline for harm.
- After the study population is expanded to include disease severity stratum 2, these analyses are performed by disease severity stratum.

At the discretion of the DSMB, these safety reports will be prepared at a frequency they specify, for example, weekly. The DSMB may also request additional data summaries.

10.2 Early Assessment of Futility

10.2.1 Interim Monitoring Guidelines for Early Assessment of Futility

Early in the trial, enrolment is restricted to participants in disease severity stratum 1. When Day 5 data for the first (approximately) 300 participants (150 per study arm) are available, the DSMB will review interim data and use pre-specified guidelines for early evidence of sufficient activity of the investigational agent that justifies continuing enrolment for the agent and expanding eligibility criteria to include participants in disease severity stratum 2 as well as stratum 1. Because the risk-benefit trade-off may be more complex than can be captured in pre-specified guidelines, decisions to terminate an agent for futility will include a broad assessment of the available data, and may be postponed until more data is available.

The early futility monitoring uses two co-primary outcomes, denoted by "pulmonary" and "pulmonary+", assessed on Day 5. Both are ordered categorical outcomes with 7 categories, described in section 4.1 of the protocol and in Appendix A to this SAP. The pulmonary outcome considers largely respiratory-related disease, similar to the ordinal outcome in the ACTT-1 trial.¹² The pulmonary+ outcome has the same categories for pulmonary complications (e.g., requirements for oxygen), and additionally includes extra-pulmonary outcomes such as thrombotic, myocardial, and cerebral complications of COVID-19.

Guidelines for the early futility assessment are as follows:

- a. If the investigational agent is superior to placebo (i.e., p ≤ 0.3 for a one-sided test) in both the pulmonary+ and pulmonary intermediate ordinal outcomes, then enrolment for the agent will expand to complete the trial.
- b. If there is insufficient evidence for superiority versus control (i.e., one-sided p>0.3) in each of the two outcomes, then stop randomization.
- c. If there is evidence (1-sided p < 0.3) for an association for one endpoint and not the other, then the agent may or may not advance depending on the risk/benefit profile emerging from the data at this early stage. If the effect estimate for both outcomes is on the side of benefit, the preference would be towards advancing the agent and expanding enrollment to include disease severity stratum 2.

The DSMB will be asked to review whether the discordance is attributable to a positive or negative effect on extra-pulmonary organ dysfunction (the difference in the two ordinal scale categories, the conditions included in pulmonary+ but not in the pulmonary endpoint), and whether the same ordinal outcomes assessed on other days yield similar results, and weigh the risk/benefit profile. For example, if there is a significant positive effect on the pulmonary score and the lack of significant effect on the pulmonary+ score is driven by a lack of difference in the milder thrombotic symptoms in category 4 of the pulmonary+ scale (e.g. deep venous thrombosis) and there is no evidence of any raised risk of thrombosis overall, the agent will advance. Conversely, if the agent is superior to the control group with respect to the pulmonary+ outcome or has a concerning safety profile, it will not advance.

Analyses of the primary efficacy endpoint, time to sustained recovery, will also be provided to the DSMB, as supporting information. These analyses are described in section 8.1.

If available, subgroup analyses by nAb status at study entry (nAb negative or positive) will also be provided.

10.2.2 Analyses of the Pulmonary and Pulmonary+ outcomes on Day 5

- Treatment groups will be compared by intention to treat.
- For each of the two ordinal outcomes, the number and percentage of participants in each of the categories on Day 5 will be tabulated, and the OR of the active versus control group will be estimated using a proportional odds model with indicators for the investigational agent group (active versus control) and for the categories of the ordinal pulmonary+ outcome at baseline (to adjust for baseline severity of illness).² The model will be stratified by site pharmacy.

The summary tables will show the adjusted summary OR with 95% CI, estimated as described above, as primary analysis. In addition, the unadjusted summary OR with 95% CI will be shown as sensitivity analysis (estimated using a proportional odds model without adjustment for the pulmonary+ baseline category or site pharmacy). In the case that the adjusted OR differs substantially from the unadjusted OR, the reason for the deviation will be explored.

Comments:

- Results will be presented such that OR>1 favors the investigational agent, denoting higher odds of more favorable disease categories in the group randomized to investigational agent compared with control.
- In order to avoid overestimating the proportion of participants who died, participants who died prior to Day 5 will only be included in the Day 5 summaries of the pulmonary and pulmonary+ outcomes if their time from randomization to cut-date is at least 5 days, and similarly for analyses on other days. Mortality is a key secondary endpoint and will be summarized cumulatively as an additional analysis.
- For the initial futility analysis, the tests comparing the investigational agent versus placebo will be performed using a (1-sided) type 1 error rate of 30%. This means, the investigational agent will be considered "superior" to the control with respect to the pulmonary (or pulmonary+) outcome, if the estimated summary OR is greater than 1, and the p-value < 0.30.

The summary reports will show the estimated summary OR with 95% CI, the signed Z-value for the test statistic comparing the treatment groups, and the one-sided p-value for superiority, calculated in the primary analysis (i.e., using the proportional odds model that is adjusted for the pulmonary+ category at baseline and stratified by site pharmacy, as described above). As sensitivity analysis, these values will also be calculated using the unadjusted proportional odds model and included in the summary report.

Comment: At the recommendation of the FDA, for monoclonal antibodies studied, patients requiring high-flow oxygen or mechanical ventilation (invasive or non-invasive) are not eligible for enrolment unless the investigational agent passes the initial futility assessment. At that time, the FDA will be consulted. This was done for AZD7442 after it passed the initial futility

assessment and the FDA allowed expansion of enrollment. This initial enrollment restriction does not apply to investigational agents other than monoclonal antibodies.

If eligibility is restricted to disease severity stratum 1, adjusting the treatment comparison for the pulmonary+ outcome at baseline is identical to adjusting for the following categories defined by oxygen requirement:

- No supplemental oxygen (pulmonary+ category 2)
- Supplemental oxygen < 4 L/min (or < 4 L/min above premorbid requirements) (pulmonary+ category 3)
- Supplemental oxygen > 4 L/min (or > 4 L/min above premorbid requirements, but not high-flow oxygen) (pulmonary+ category 4)
- To supplement the overall summary odds ratios for the 7-category outcomes, each dichotomized definition of improvement that can be formulated from the components of the ordinal outcomes will be considered separately; for example, treatment groups will be compared for the proportions of participants in category 1 on Day 5, proportions in categories 1 or 2 ("best two categories"), in categories 1-3, etc. Proportions will be tabulated, and odds ratios for active versus control groups will be estimated with 2-sided 95% CIs using logistic regression models. These analyses need to be interpreted with caution, because they are not adjusted for inflation of type I error due to multiple comparisons.
- Subgroup analyses will be carried out for the Pulmonary and Pulmonary+ outcomes on Day 5, to supplement the early futility analyses. The goal is to determine whether the treatment effect differs across subgroups, and to aid the DSMB in considerations on whether there are safety concerns in specific subgroups. Principles for subgroup analyses are described in section 9.1; here, subgroup analyses are based on the proportional odds models. In particular, heterogeneity of the treatment effect across the baseline pulmonary+ categories will be assessed.
- After an investigational agent has passed initial futility assessment and enrollment has been expanded to include participants in disease severity stratum 2, treatment comparisons for the pulmonary and pulmonary+ outcomes on Day 5 continue, and will be performed separately for each of the two disease severity strata, to assess safety for the more severely ill participants in stratum 2.

Missing data: Unknown outcome status for the pulmonary or pulmonary+ outcomes on Day 5:

The following items describe how missing data will be treated for the primary analyses of the pulmonary or pulmonary+ outcomes on Day 5. As needed, these methods may be also applied to analyses at other time points (e.g., Day 7).

Interim analyses:

 Only participants with Day 5 data for the pulmonary outcome will be included for the Day 5 comparisons. The number and proportion of participants with unknown outcome status will be summarized.

Comment: If the cut date is less than 10 days before the data freeze date, Day 5 data for the ordinal outcomes are considered "missing" only for participants with at least 10 days of administrative follow-up.

- Final analyses after completion of the trial:
 - If Day 5 data are missing for a substantial proportion of participants (e.g., more than 5% of the mITT cohort), multiple imputation will be used to impute missing Day 5 data for the pulmonary and pulmonary+ outcomes. For the imputation, the following baseline covariates will be considered in addition to the indicator for treatment group: age, sex, country, duration of symptoms prior to enrollment, status of the ordinal pulmonary (or pulmonary+) outcome, and presence of comorbidities. Ten rounds of imputation will be used to estimate the summary odds ratio.
 - The number and proportion of participants with missing data will be reported.

Sensitivity analyses

- As sensitivity analyses, the treatment groups will be compared by **modified intentionto-treat (mITT)** after excluding participants who did not receive any of the assigned investigational agent (active or control). This mITT analysis will be provided at important decision points, e.g., when the test statistic approaches the monitoring boundary, and for the final analyses after completion of the trial.
- Treatment groups will be compared for the pulmonary and pulmonary+ outcomes on Days 1-7, to monitor the consistency of the treatment effect over time.

Assessment of model assumptions

- For the pulmonary and pulmonary+ outcomes at Day 5, the proportionality assumption
 of the odds ratio will be assessed (by including the interaction between the treatment
 group indicator and indicators for the Day 5 cumulative ordinal categories in the model,
 as well as the interactions between the treatment group indicator and the indicators for
 the strata by baseline pulmonary+ categories and site pharmacy; this corresponds to
 testing for separate slopes using a partial proportional odds model, see section 3 under
 "ordered categories"). If there is evidence for non-proportionality, the summary odds
 ratio in the proportional odds model will still be used to quantify the treatment effect, and
 the analyses of the dichotomized ordinal outcome categories will be used to help
 interpret the treatment effect.
- The sample size of 300 (150 per study arm) is sufficient to detect a summary OR of 1.60 for the comparison of the investigational agent versus control for each of the two ordinal outcomes with 95% power. The power of the tests depends on the hypothesized OR and the hypothesized distribution in the control group used for the sample size calculations. At the time of the early futility review, the deviation of the observed distribution from the hypothesized distribution in the control arm will be assessed, and the impact on the power of the trial will be estimated.

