1.4 Sample Size Estimates

The planned sample size for each pairwise comparison is 1,000 participants (500 participants in each group). The sample size is sufficient to detect a recovery rate ratio (RRR) of 1.25 for time to sustained recovery with 90% power, using a one-sided test with a significance level of 0.025. The treatment groups are compared using Gray's test with ρ =0, the competing risks analogue of the log-rank test.

Sample size calculations are described in detail in Section 6.3 of the protocol.

Blinded sample size re-estimation will be carried out before enrollment is complete to determine whether the planned sample size of 1,000 participants followed for 90 days will yield the planned number of 843 primary events. The blinded sample size re-estimation does not involve unblinding of the treatment difference. It will be based on the pooled outcome data. Sample size may be increased to achieve the event target in the planned follow-up of 90 days. A

sample size increase may also be considered in order to achieve the event target before all participants are followed for 90 days.

When 300 participants (150 per study arm) are enrolled and have Day 5 outcome data, an early futility assessment is planned. This assessment will be based on two ordinal outcomes, denoted as "pulmonary" and the "pulmonary+"; both are ordered categorical outcomes with 7 categories, assessed on Day 5 (the two outcomes are described in Appendix A). Treatment groups will be compared using proportional odds models. With 300 participants, the early futility assessment is powered to detect a summary OR=1.60 with power of 95%, using a one-sided test with significance level of 0.30.¹ Given the two-outcome decision rules, an investigational agent with a summary OR=1.60 at Day 5 for both outcomes, would pass the futility assessment with a power between 93% and 98%, and a type I error between 0.21 and 0.39.

2 Interim DSMB Reviews: Goals and Format

Each investigational agent versus control will be reviewed as a separate clinical trial; separate data reports will be prepared for each investigational agent and the corresponding randomized (pooled) placebo group.

Goals of the interim reviews:

- Protect the safety of study participants.
- Advise on stopping or modifying the trial for efficacy, for patient safety in case of emerging data on harm, or for futility.

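### SAP 10.2.1 makes superiority on pulmonary+ a reason not to advance an agent, against its own guideline (c)

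*SAP*

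**What the plan says.** SAP section 10.2.1 sets three guidelines for the early futility look, based on the pulmonary and pulmonary+ outcomes at Day 5:

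- **(a)** Superior on both outcomes (one-sided p at or below 0.3): enrolment expands.
- **(b)** Superior on neither: randomization stops.
- **(c)** Evidence on one outcome only: the decision depends on the emerging risk/benefit profile. "If the effect estimate for both outcomes is on the side of benefit, the preference would be towards advancing the agent".

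The paragraph that follows expands on (c). It asks the DSMB to "review whether the discordance is attributable to a positive or negative effect on extra-pulmonary organ dysfunction". Its first example is an agent with a significant pulmonary effect but no significant pulmonary+ effect, where the gap comes from the milder thrombotic events and thrombosis risk is not raised overall. That agent advances. The contrasting sentence then says: "if the agent is superior to the control group with respect to the pulmonary+ outcome or has a concerning safety profile, it will not advance".

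Section 10.2.2 fixes the terms. On direction: "Results will be presented such that OR>1 favors the investigational agent". An agent counts as superior on either outcome "if the estimated summary OR is greater than 1, and the p-value < 0.30".

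Section 1.4 gives operating characteristics for the two-outcome rule. An agent with OR=1.60 on both outcomes "would pass the futility assessment with a power between 93% and 98%, and a type I error between 0.21 and 0.39".

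**The concern.** Under the section 10.2.2 definition, superior can only mean benefit. The sentence therefore treats a benefit on one of two co-primary futility outcomes as grounds for not advancing, on a par with a safety concern.

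This conflicts with guideline (c), which treats the two outcomes alike and leaves the decision open. It also sits badly with the question that opens the same paragraph: superiority on pulmonary+ alone is the pattern that a positive extra-pulmonary effect would produce, yet that pattern is barred.

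At stake is a go/no-go decision. For an agent superior on pulmonary+ only, the DSMB would hold two written instructions that can point in opposite directions.

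**Working it through.** **1. The text, case by case.** Superior means OR>1 with one-sided p<0.30.

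| Day 5 result | Guidelines (a)–(c) | Contrasting sentence, read literally |
|---|---|---|
| Superior on both | Expand, by (a) | Not addressed if confined to discordant cases |
| Superior on neither | Stop, by (b) | Not addressed |
| Pulmonary only | Risk/benefit, by (c) | Not addressed, unless safety is a concern |
| Pulmonary+ only, pulmonary estimate unfavourable | Risk/benefit, by (c) | Does not advance |
| Pulmonary+ only, pulmonary estimate favourable but p>0.3 | Advancing preferred, by (c) | Does not advance |

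The last row is a direct conflict. In the row above it, a categorical rule replaces a discretionary one. If the sentence were read outside the discordant setting, it would contradict (a) as well.

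**2. Reproducing the section 1.4 ranges.** Inputs: one-sided alpha 0.30 per outcome (10.2.1 and 10.2.2); 95% power per outcome at OR=1.60 with 300 participants (1.4 and 10.2.2); joint null pass probability 0.21 (lower limit in 1.4).

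The lower limits should be P(superior on both) and the upper limits P(superior on at least one). Under the null no model is needed:

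P(at least one) = 0.30 + 0.30 − 0.21 = 0.39, the stated upper limit.

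For OR=1.60, take the two test statistics as bivariate normal with unit variances. The cut-off is z(0.70) = 0.524. The mean that gives 95% power is 0.524 + 1.645 = 2.169. The SAP gives no correlation; solving P(both | null) = 0.21 gives 0.795, which is assumed to hold at OR=1.60 too. Then:

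- P(both) = 0.9245 (stated 93%)
- P(at least one) = 0.95 + 0.95 − 0.9245 = 0.9755 (stated 98%)

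The upper limit agrees after rounding and the lower limit is within about half a point. The stated upper limits therefore count agents superior on pulmonary+ alone as able to pass.

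**3. Effect of the literal sentence.** If such agents never advance, an agent can pass only when it is superior on pulmonary. The ceiling is then the single-outcome probability, whatever the correlation: 0.30 under the null and 95% at OR=1.60.

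**4. How often the pattern arises.**

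| | Null | OR=1.60 |
|---|---|---|
| Pulmonary+ only | 0.30 − 0.21 = 0.090 | 0.95 − 0.9245 = 0.0255 |
| of which pulmonary estimate favourable (Z between 0 and 0.524) | 0.0604 (67%) | 0.0211 (83%) |

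Because 0.21 is rounded, the joint null probability was varied:

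| Joint null probability | Correlation | Pulmonary+ only, null | Pulmonary+ only, OR=1.60 |
|---|---|---|---|
| 0.205 | 0.772 | 0.095 | 0.0268 |
| 0.215 | 0.816 | 0.085 | 0.0242 |

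The SAP's rounded percentages alone give 95 − 93 = 2 or 98 − 95 = 3 points at OR=1.60.

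**5. If the sentence were reversed.** Suppose a pulmonary-superior agent is stopped when its pulmonary+ result is unfavourable, and every other discordant agent advances. The upper limits depend on how unfavourable is defined:

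- Pulmonary+ OR below 1: 0.390 − 0.030 = 0.360, and 0.9755 − 0.0044 = 0.971.
- One-sided p<0.30 for harm on pulmonary+: 0.390 − 0.006 = 0.384, and 0.9755 − 0.0004 = 0.975.

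The full 0.39 is reached only if every discordant agent advances. At OR=1.60 the second definition differs from that case by only 0.0004.

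**The case against.** The strongest reply is that little depends on this sentence. Section 10.2.1 presents guidelines, not binding rules: "decisions to terminate an agent for futility will include a broad assessment of the available data, and may be postponed". A DSMB is unlikely to stop an agent because it did better than placebo, so the percentages above are frequencies of a data pattern, not of wrong decisions. Appendix G records 496 participants randomized to the MP0420 comparison, so that agent is past the look at about 300, and the documents name no later agent still to reach it. All of this stands, and it limits the severity.

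A second reply is that (c) permits not advancing a discordant agent, so the head-on conflict is confined to cases where the pulmonary estimate is also favourable. That is fair; the 6.0% and 2.1% figures are the ones that measure it. In the remaining cases a fixed rule still replaces a discretionary one.

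Third, the section 1.4 ranges are outer limits for a discretionary rule, and the literal reading stays inside them. Section 1.4 is therefore not in error; it is supporting evidence that its authors counted agents superior on pulmonary+ alone as able to advance. The correlation is back-solved from a rounded figure, so the third decimal should carry no weight.

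Finally, the asymmetry could be deliberate. No reason for penalising a pulmonary+ benefit appears anywhere in the documents, and the pairing with a safety concern points to a slip. The intended word cannot be established from the text, and the master protocol sections that the SAP cites were not available to check.

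**Conclusion.** The concern holds. As written, the sentence makes benefit on a co-primary futility outcome a reason not to advance, and nothing else in the documents corrects it. It opposes guideline (c) directly in about 6.0% of trials under the null and 2.1% at OR=1.60. It overrides the discretion in (c) in about 9% and 2–3% respectively.

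The 9% and the ceilings of 0.30 and 95% follow from the SAP's own figures. The other frequencies rest on bivariate normality and a correlation of about 0.8 that also applies under the alternative.

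It should be fixed, but its reach is bounded. The primary endpoint, sample size and final alpha are unaffected, and the correction matters for the platform guidance and any agent yet to reach this look, not for decisions already taken on MP0420.

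**What to change.** Reconcile the contrasting sentence in SAP section 10.2.1 with guideline (c):

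1. Reword it so that an unfavourable pulmonary+ result, or a concerning safety profile, weighs against advancing. The sponsor should confirm that this was the intention and define the term, for example whether it means an OR below 1 or a one-sided test for harm. Simply writing *not superior* would need a qualifier, because the preceding example advances an agent without a significant pulmonary+ effect.
2. State that superiority on pulmonary+ alone is handled under guideline (c). If the sponsor did intend an asymmetric rule, say so, give the reason and amend (c) to match.
3. Preferably, add a clause to section 1.4 saying that the upper limits of 0.39 and 98% assume every discordant agent advances, or restate them for the corrected rule.

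The cost is one sentence and, if item 3 is taken up, one clause. No new data are needed, and neither the sample size nor any test changes.
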